7. RECRUITMENT

Please state clearly how the participants will be identified, approached and recruited.

Note: Attach a copy of any poster(s), advertisement(s) or letter(s) to be used for recruitment.

The patients will be recruited from Outpatient Clinic of faculty of medicine, South Vally University.

8. CONSENT

Describe the process that the investigator(s) will be using to obtain valid consent. If consent is not to be obtained explain why. If the participants are minors or for other reasons are not competent to consent, describe the proposed alternate source of consent, including any permission / information letter to be provided to the person(s) providing the consent.

I am freely and voluntarily consent to participate in a research program under the direction of M.Sc.

A thorough description of the procedure has been explained and I understand that I may withdraw my consent and discontinue participation in this research at any time without prejudice to me.

Date Participant

قرار
 قر ان الموقع أدنزاوقأي وفق ت علي الأنترالفب برن امج ال ح شحت إشرفا ال باحث
 وقد تم شرح خطوات ال ح شتل ي بلق ف صيريل ول ه من حقني أن انسحب من ال دراس في أي وقت أثناء
 العشا ارك

تايخ

Note: Attach a copy of the Consent Form, Participant Information Sheet (if applicable).

PARTICIPANT WITHDRAWAL

a) Describe how the participants will be informed of their right to withdraw from the project.

All parents will sign a written consent form after receiving information about the study purpose, whole procedures, possible benefits, privacy and use of data to ensure full cooperation. Parents will understand that they may withdraw their consent and discontinue participation in the research at any time without prejudice to them.

b) Explain any consequences for the participant of withdrawing from the study and indicate what will be done with the participant's data if they withdraw.

All data of withdrawn participant will be excluded from analysis.

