5. CONDUCT OF PROJECT

Please give a description of the research methodology that will be used

- Nerve conduction studies (NCS) and somatosensory-evoked potentials (SSEPs) were used to assess peripheral neuropathy pre and post intervention.
-

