6. PARTICIPANTS AS THE SUBJECTS OF THE RESEARCH

Describe the number of participants and important characteristics (such as age, gender, intellectual ability etc.). Specify any inclusion/exclusion criteria to be used.

Subjects:

Eighty children with tumors were enrolled in this study and were assessed for eligibility. Their aged ranged from six and fourteen years. They were assigned randomly into two equal groups. Group (A) study group received the same medical care and shockwave, three times / weak for three successful months. And group (B) control group received medical care and standard chemotherapy only. Nerve conduction studies (NCS) and somatosensory-evoked potentials (SSEPs) were used to assess peripheral neuropathy pre and post intervention. All children were assisted before and after three months of intervention.

Inclusion criteria:

1. Their age will ranging from six to fourteen years.
2. Children participated in this study will from both sexes.
3. Children receiving chemotherapy as primary treatment, postoperative surgical removal of tumors or with conjunction with radiotherapy
4. All children have polyneuropathy caused by chemotherapy.

Exclusion criteria:

1. Children with Epilepsy.
2. Children with blood clotting disorder.
3. Children have Open wounds / broken skin
4. Children with severe cardiac disease
5. Uncooperative patients.

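### Excluding all data of every withdrawn child, even where the family still permits use of the data, can bias the randomised comparison and discards collected data

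*Protocol*

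**What the plan says.** Section 8, Participant withdrawal, item b, asks what happens to a participant's data on withdrawal. The whole answer is "All data of withdrawn participant will be excluded from analysis".

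Item a describes the right itself: parents are told that "they may withdraw their consent and discontinue participation in the research at any time without prejudice to them". The consent statement in the same section reads "I understand that I may withdraw my consent and discontinue participation in this research at any time without prejudice to me". Parents sign after "receiving information about the study purpose, whole procedures, possible benefits, privacy and use of data". None of these texts asks for, or promises, removal of data already collected.

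On design, section 6 states "They were assigned randomly into two equal groups". Group A "received the same medical care and shockwave, three times / weak for three successful months", while Group B has no added sessions. (Section 6 names a different intervention from the study's stated aim; that is a separate matter.) Section 5 says that nerve conduction studies and evoked potentials "were used to assess peripheral neuropathy pre and post intervention", and section 6 adds "All children were assisted before and after three months of intervention". So there is one baseline and one three-month measurement, and nothing between.

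No section names an analysis set, provides for assessment after withdrawal, or makes an exception to the exclusion.

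**The concern.** This is a stated analysis rule, not a detail left to an unseen SAP. It makes membership of the analysis depend on something that happens after randomisation. The visit burden falls on Group A alone, so families may leave the two arms at different rates and for different reasons, including how the child is doing. If so, the children left in each arm are no longer comparable, and the difference between arms mixes any treatment effect with selection. The bias can go either way.

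The rule also does not separate three events: stopping the sessions, leaving follow-up, and revoking permission to use data. On a narrow reading a child who only stops sessions is not withdrawn and is untouched by the rule. On a broad reading that child is excluded too.

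There is a practical consequence as well. A team that will discard a withdrawn child's data has no reason to seek the three-month test, and an outcome not measured then cannot be recovered by a later SAP.

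**Working it through.** The protocol has no sample-size, power or dropout calculation, so there is no figure to reproduce.

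**From the protocol:** 80 children, two equal groups, hence 40 per arm; assessment at baseline and three months.

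**Assumed throughout, for illustration:** outcome in SD units, SD unchanged among the children analysed, two-sided 5% t-test, no true effect (except in step 4). Group A withdrawers lie δ below the full Group A mean, with δ = 0.5, and δ = 1.0 in brackets. Rejection rates come from the noncentral t with noncentrality bias / √(1/n_A + 1/n_B).

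**1. Effect due to the rule alone.** k Group A children withdraw after the three-month test and their measured outcomes are discarded; none in Group B.

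Bias = kδ/(40 − k), n = 40 − k against 40.

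| k | Bias (SD) | False positives |
|---|---|---|
| 1 | 0.5/39 = 0.013 (0.026) | 5.04% (5.15%) |
| 2 | 2 × 0.5/38 = 0.026 (0.053) | 5.2% (5.6%) |
| 4 | 4 × 0.5/36 = 0.056 (0.111) | 5.7% (7.6%) |

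**2. Early withdrawal.** 8 of 40 leave Group A; 2 of 40 leave Group B at random. Suppose k of the 8, a random subset, have or would accept a three-month assessment and are kept.

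Remaining bias = (8 − k)δ/(32 + k), n = 32 + k against 38. The rule's share is the bias with all 8 excluded, 8δ/32 = 0.25δ, minus the remaining bias.

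| k kept | Remaining bias (SD) | False positives | Rule's share (SD) |
|---|---|---|---|
| 0 | 0.125 (0.250) | 8.1% (17.7%) | 0 (0) |
| 2 | 0.088 (0.176) | 6.6% (11.4%) | 0.037 (0.074) |
| 4 | 0.056 (0.111) | 5.6% (7.6%) | 0.069 (0.139) |
| 8 | 0 (0) | 5.0% (5.0%) | 0.125 (0.250) |

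The top row is the effect of informative missing outcomes in general. The rule is responsible only for what could have been recovered.

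**3. Variations.**
- The 4 who are assessed are milder cases with deficit δ/2: remaining bias (8 − 2)δ/36 = 0.083 (0.167) SD, false positives 6.4% (10.9%).
- Only 4 of 40 leave Group A: 5.6% (7.6%) with all excluded; 5.1% (5.6%) if half are assessed and kept (bias 2δ/38, 38 against 38).
- Withdrawal unrelated to outcome, or the same share with the same selection in both arms: bias 0, false positives 5.0%.
- Withdrawers better rather than worse: the sign reverses.

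**4. Precision.** With an assumed true effect of 0.634 SD, 40 per arm gives 80% power. Losing 8 per arm at random gives 32 per arm and 70%. Recovering 2 or 4 per arm gives 34 or 36 per arm and 73% or 76%.

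**5. Checks.** A simulation of step 2 (200,000 runs, withdrawal driven by a latent variable correlated with outcome) gave 8.1, 6.7, 5.6 and 4.9% (18.8, 11.6, 7.6 and 5.0%) with 0, 25, 50 and 100% assessed at random. It is somewhat above the formula in the most extreme case, where selection narrows the spread among the children left and the fixed-SD formula ignores this.

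In one simulated data set, the baseline-adjusted group difference was 0.7515 in completers and still 0.7515 after imputing baseline-only children from group and baseline; with all outcomes known it was 0.5021. In that check, keeping baseline data alone did not repair the estimate. The three-month outcome is what matters.

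**The case against.** The strongest objection is that the rule's own effect is small on this schedule. With only two measurements, a child who leaves before month three has no outcome to discard, and that gap would exist without the sentence. This stands. What the rule surely throws away is the outcome of a child withdrawn at or after the final test, probably a rare event. The larger shares in step 2 depend on families agreeing to an assessment that the protocol does not plan for withdrawn children.

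A second objection is that withdrawn consent may reasonably be read to cover use of data, so that exclusion is a commitment to the families of minors. An information sheet that is not shown could say so. This is fair as far as it goes, but the text shown speaks of ending participation, never of deleting data, and the exclusion is automatic. The change below still removes data wherever a parent asks for that.

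A third is that reporting withdrawals by arm and running sensitivity analyses belong in a SAP. That is accepted: they are useful additions, and the point does not depend on them.

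**Conclusion.** The concern holds. The protocol fixes an unconditional exclusion after randomisation, nothing in it softens the rule, and the consent wording shown does not require it. The rule should be changed, but its effect should not be overstated.

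The part due to the rule alone is modest: false positives of 5.2% to 7.6% when 2 to 4 measured Group A outcomes are discarded and those children are 0.5 to 1.0 SD worse than their arm's mean. It is nil if no outcome is recoverable, and larger if many early leavers would accept the three-month test. It becomes bias only if withdrawal relates to outcome and differs by arm; otherwise it costs precision. Every withdrawal rate, deficit, effect and test level used here is assumed, so for this trial the size and direction are unknown.

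**What to change.** Replace the sentence in section 8, item b, with wording such as:

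> Stopping the intervention is not withdrawal from the study; these children keep the planned three-month NCS/SSEP assessment. A family that withdraws will be asked whether it agrees to that assessment. Data already collected are kept and analysed in the randomised group, and removed only if the parent expressly withdraws permission for their use.

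Align the consent statement and the information on use of data with this.

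Two additions are advisable. Report the number, timing and reasons of withdrawals by arm. Because some early leavers will have baseline data only, add a sensitivity analysis that shifts their missing three-month outcomes in either arm, for example by 0 to 1 SD.

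The cost is a protocol sentence, a change to the consent form and information with the approval that needs, and some follow-up effort for families who agree. No new type of assessment is required. Some outcomes will stay missing, and this change does not remove that part of the bias.

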9. CONFIDENTIALITY

- a) Will all participants be anonymous? Yes No
- b) Will all data be treated as confidential? Yes No

Note: Participants' identity/data will be confidential if an assigned ID code or number is used, but it will not be anonymous. Anonymous data cannot be traced back to an individual participant.

10. SIGNIFICANCE/BENEFITS

Outline the potential significance and/or benefits of the research

The use of freezing temperatures for analgesia has been recorded for thousands of years. Modern cryotherapy has slowly become a well-established treatment option for peripheral neuralgias and neuropathic pain conditions. Cryoneurolysis induces peripheral nerve damage and causes nerves to undergo axonotmesis followed by Wallerian degeneration. Nerve regrowth occurs but may not lead to permanent pain relief. The therapy continues to be optimized and is best used for well-defined small nerves that are easy to target. The use of cryotherapy has been indicated for intercostal neuralgia, occipital neuralgia, trigeminal neuralgia, phantom limb pain, obturator neuralgia, genitofemoral neuralgia, and intractable perineal pain.

11. RISKS

Outline any potential risks to **INDIVIDUALS**, including research staff, research participants, other individuals not involved in the research and the measures that will be taken to minimise any risks and the procedures to be adopted in the event of mishap

All patients will be given an explanatory session before starting evaluation procedures to be aware about different steps of test.
--

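### Section 8(b) drops all data of withdrawn children from analysis, while the text shown records neither harms nor reasons for withdrawal and gives no mishap procedure

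*Protocol*

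**What the plan says.** Section 8 (Consent, Participant Withdrawal) deals with withdrawal in two items. Item a describes the right to withdraw: "Parents will understand that they may withdraw their consent and discontinue participation in the research at any time without prejudice to them". Item b states what then happens to the data: "All data of withdrawn participant will be excluded from analysis". The rule has no qualification by timing, reason or type of data.

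The prompt in Section 11 (Risks) asks for potential risks and for "the measures that will be taken to minimise any risks and the procedures to be adopted in the event of mishap". The whole answer shown is: "All patients will be given an explanatory session before starting evaluation procedures to be aware about different steps of test".

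Section 6 gives the setting. Eighty children aged six to fourteen are randomised into two equal groups, and one inclusion criterion reads "All children have polyneuropathy caused by chemotherapy". On treatment and follow-up it says "Group (A) study group received the same medical care and shockwave, three times / weak for three successful months" and "All children were assisted before and after three months of intervention". The outcome measures in Sections 5 and 6 are nerve conduction studies and somatosensory-evoked potentials.

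**The concern.** Withdrawal happens after randomisation and can depend on the treatment. Parents may withdraw a child because the sessions hurt or caused injury, or because the neuropathy is not improving. Neither reason need be equally common in the two arms, since only Group A receives the sessions. A rule that deletes every withdrawn child therefore selects the analysed groups on something that treatment can affect, and the protection given by randomisation is weakened.

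The rule also combines badly with what is not collected. If a child is harmed and withdrawn in mid-course, the text shown gives staff no procedure to follow and no place to record the event or the reason. Anything that had been noted would then be excluded. At the end of the trial, nobody could say how many children left because of harm, or from which arm.

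**Working it through.** The protocol states no dropout, harm or withdrawal rate, so there is no figure to reproduce. The check compares the sections and then shows the mechanism of the rule on an assumed count.

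**1. Section 11, prompt against answer.**
- Potential risks: none of the intervention is named.
- Measures to minimise risk: a session explaining the tests. The Section 6 exclusions (epilepsy, clotting disorder, open wounds, severe cardiac disease) are at most implicit precautions. They act before enrolment and are tied to no stated risk.
- Procedure in the event of mishap: none.

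**2. Section 8, items a and b together.** Item a describes withdrawal as parents withdrawing consent and discontinuing participation. Item b then excludes everything. The text does not say whether a child who only stops the sessions counts as withdrawn. If staff read it that way, a child who could still be tested at three months is lost as well.

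**3. What the rule removes, given two assessment times.**
- A child withdrawn before three months has a baseline but no outcome. The damage to the efficacy comparison comes mainly from the missing outcome. A complete-case pre-post comparison would drop this child even without item b.
- A child who stops sessions, stays under consent and could be tested at three months is lost needlessly if classed as withdrawn.
- A child whose parents withdraw after the three-month test loses an outcome already measured.
- In every case, any adverse event and any reason for leaving go too.

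**4. Illustration for an account of harms (assumed count, not in the protocol).** Group A has 80 / 2 = 40 children. Suppose h = 4 are harmed and w of these withdraw. The proportion harmed among analysed children is (h − w) / (40 − w):

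| w | Analysed data | Proportion |
|---|---|---|
| 0 | 4/40 | 10.0% |
| 2 | 2/38 | 5.3% |
| 4 | 0/36 | 0% |

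Each child withdrawn because of harm leaves both numerator and denominator, so the proportion can only fall. The direction follows from the rule; the size depends entirely on the assumed h and w.

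**The case against.** **No harm analysis is planned.** The stated aim is efficacy, the stated measures are neurophysiological, and no safety endpoint or safety claim appears. A reader might infer that the rule will make the intervention look safer than it was. The protocol does not support this, because it describes no harm dataset for the rule to distort. This stands: the table above shows what would happen to any account of harms, not to a planned result. The gap is that harms are not recorded at all, and that the rule would exclude them if they were.

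**Lost baselines are not the main bias.** A reader might blame the efficacy bias on discarded baseline data. That is the wrong cause, as step 3 shows. Keeping pre-withdrawal data alone would not repair the comparison; three-month follow-up of children who only stop sessions is also needed.

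**Session counts do not size the defect.** Three sessions a week for an assumed 12 to 13 weeks is 36 to 39 per treated child, or 1,440 to 1,560 in 40 children if all attend. This measures exposure, not risk or bias. Nor does the protocol say that harm is sought at sessions. Group B has clinical contact too, through medical care and chemotherapy, at an unstated frequency.

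**Item b is an ethics-form answer.** Not using data after consent is withdrawn is a common choice that protects participants. This stands in part: it limits how much can be retained, but it does not justify excluding data whose use parents would allow.

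**Parts of the file are not shown.** Section 8 describes the parent information as follows: "All parents will sign a written consent form after receiving information about the study purpose, whole procedures, possible benefits, privacy and use of data". Benefits are listed and risks are not, so a reader might infer that parents are told of no risks. The consent pages are not shown and may name them. Other parts of the protocol were also removed, so the absence of a mishap procedure is established only for the text shown. Neither limit changes the wording of item b.

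**Nerve damage in Section 10.** The remark there concerns cryoneurolysis. It is not shown to be the treatment given, which Section 6 calls shockwave, so it proves no risk of this intervention.

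**Conclusion.** The point holds in a limited form. Section 8(b) is a stated, unconditional rule that, if followed, removes randomised children from the comparison, including any withdrawn because of harm or poor response. It is not a detail left to a statistical analysis plan: a plan that kept these data would contradict the protocol. In the text shown, nothing provides for recording adverse events or reasons for withdrawal, and Section 11 leaves the mishap part of its prompt unanswered.

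The size is unknown. The effect is nil if nobody withdraws. On efficacy, bias arises if withdrawal is related both to arm and to outcome. On harms, information is lost whenever a harmed child withdraws. The conclusion assumes that item b is applied literally and that no unseen section overrides it. The missing list of intervention risks in Section 11 is a lesser matter of incomplete detail.

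**What to change.** - Replace Section 8(b): data collected before withdrawal, including adverse events and the reason for withdrawal, are kept and reported by randomised arm as far as consent allows.
- State that a child who only stops sessions is not withdrawn, is assessed at three months and is analysed in the assigned group.
- Record adverse events in both arms with the same questions at the same times, so that Group A's sessions do not create extra opportunities for detection.
- State in Section 11 what staff do when a child is harmed: when to stop treatment, who is told, and what care follows. Name there the risks of the treatment actually given.

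The cost is one short form with a field for the reason for withdrawal, some extra contacts in Group B, and new wording in Sections 8 and 11. Retention will be incomplete where parents refuse use of data. The number of such refusals should be reported by arm.

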4. SUMMARY OF PROPOSAL

PURPOSE:

This study aimed to assess the efficacy of cryotherapy in controlling Peripheral Neuropathy in pediatric tumor patients

BACKGROUND:

Peripheral neuropathy is a serious condition characterized by symmetrical, distal damage to the peripheral nerves that may be caused by several classes of drugs, including chemotherapeutic agents. Chemotherapy-induced peripheral neuropathy (CIPN) is an adverse effect estimated to occur in up to 40% of patients undergoing chemotherapy, with its incidence increasing in patients being treated with multiple agents. Pharmacists play a pivotal role in the prevention and management of CIPN by recommending evidence-based pharmacologic and non-pharmacologic strategies appropriate for the individual patient. Peripheral neuropathy (PN) is a systemic disease characterized by symmetrical, distal damage to the peripheral nerves that negatively impacts patient quality of life (QOL). Prolonged symptoms associated with PN can cause pain, interfere with functional ability (e.g., dressing, driving, house-work), and disrupt emotional health.

HYPOTHESES:

H0 there is no significant difference of cryotherapy in controlling Peripheral Neuropathy in pediatric tumor patients

H1 there is a significant difference of cryotherapy in controlling Peripheral Neuropathy in pediatric tumor patients

RESEARCH QUESTION:

Is there a significant difference of cryotherapy in controlling Peripheral Neuropathy in pediatric tumor patients?

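### Group A's treatment is cryotherapy in section 4 but shockwave in section 6; section 11, as shown, covers the risks of neither, and section 8 read literally drops adverse events in children who withdraw

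*Protocol*

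**What the plan says.** Section 4 of the Protocol gives the purpose as follows: "This study aimed to assess the efficacy of cryotherapy in controlling Peripheral Neuropathy in pediatric tumor patients". Its hypotheses and research question also name cryotherapy.

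Section 6 describes the arms. For the study arm: "Group (A) study group received the same medical care and shockwave, three times / weak for three successful months". For the control arm: "And group (B) control group received medical care and standard chemotherapy only". On the timing of assessment: "All children were assisted before and after three months of intervention". On the population: "Their age will ranging from six to fourteen years" and "All children have polyneuropathy caused by chemotherapy". The same section excludes, among others, children with epilepsy, a clotting disorder, broken skin or severe cardiac disease.

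Section 8 lets parents withdraw a child at any time. Asked what happens to the data of a child who withdraws, it answers that none of them enter the analysis. It makes no exception for the reason for leaving or the type of data.

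Section 10 describes cryotherapy in general and cryoneurolysis in particular as background. It does not say which procedure these children receive.

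Section 11 asks for potential risks, "the measures that will be taken to minimise any risks and the procedures to be adopted in the event of mishap". The answer, as shown, is one sentence: "All patients will be given an explanatory session before starting evaluation procedures to be aware about different steps of test".

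**The concern.** A trial's conclusion attaches to the treatment that the experimental arm received. If the hypothesis names one modality and the arm description another, a significant difference cannot be read as evidence about cryotherapy, and a null result cannot be read as evidence against it. Staff who work from section 6 would deliver something that section 4 does not ask about.

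The same uncertainty carries into safety. The children are aged six to fourteen, already have nerve damage from chemotherapy, and are to be treated repeatedly over three months. Section 11 is where the form asks what could go wrong and what will be done about it. Its shown answer deals with the tests and not with the treatment.

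The section 8 rule adds a further problem. Children who leave because the treatment harmed them are the ones whose records matter most for safety. A rule that takes out everything about withdrawn children, applied as worded, takes those records out too.

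**Working it through.** The protocol states no figure on this point, and the check is one of text. The only arithmetic is the arm size: 80 children in two equal groups, 80 / 2 = 40 per group.

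1. **Identity of the intervention.** Purpose, both hypotheses and research question (section 4): cryotherapy. Group A (section 6): medical care plus shockwave. Group B (section 6): medical care and standard chemotherapy. Cryotherapy appears in neither arm as described. Section 5 names only the assessments, nerve conduction studies and somatosensory-evoked potentials. Section 10 returns to cryotherapy, but as general background. So no section shown reconciles the two names, and the contrast between the arms in section 6 is not the contrast in the section 4 hypothesis.

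2. **What section 11 asks and what it answers.** The prompt has three parts.
   - Potential risks: none is stated for cryotherapy or for shockwave.
   - Measures to minimise risk: an explanatory session about the test. The entry exclusions in section 6 also work as measures of this kind, although section 11 does not refer to them.
   - Procedures after a mishap: none is stated.

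   The exclusions act at entry. No section shown says whether sessions stop if an excluded condition, such as broken skin or a clotting disorder, arises during the three months.

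3. **The withdrawal rule.** Take a child in group A who has an adverse event in the second month, has it noted, and is then withdrawn by the parents. Under section 6 the second assessment comes after three months, so this child has no second nerve test. The adverse event note is then the main thing the child contributes after baseline. Section 8 as worded removes all of the child's data, and the note goes with the rest. The protocol gives neither a withdrawal rate nor an adverse event rate, so the number of events lost in this way cannot be calculated.

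**The case against.** The strongest reply has four parts.

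- **Section 8 answers a narrow question.** The form asks about data after a participant withdraws, and the only outcomes named are nerve conduction and evoked potentials. The answer can fairly be read as covering the efficacy analysis, and it does not mention adverse events. How these are tabulated, and in which population, is commonly left to a statistical analysis plan, and none was available. This stands, so the point about harms is conditional on the literal wording. A reader might infer that the trial will certainly hide harms or will record none; the protocol does not support that.

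- **Section 6 already contains safeguards.** The exclusions reduce risk, which is part of what section 11 asks for. This also stands. It would be wrong to say that the children are unprotected, or that risks cannot be specified until the name is settled: they could be listed for each of the two modalities. What remains is that none is listed for either, and that no mishap procedure is given.

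- **The section 11 gap is missing detail on an ethics form, and filling it changes no estimate.** That is largely true of section 11 taken alone. It does not reach the conflict over the intervention, which decides what the trial can conclude. Nor can the mishap procedure be left to an analysis plan, because the form asks for it here.

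- **Text may be missing.** The copy reviewed lacks the text after section 11 and any parent information sheet. Nothing can therefore be said about what parents are told.

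One more inference is tempting. Section 10 says that cryoneurolysis damages peripheral nerves, so a reader might conclude that children with neuropathy are to be given a nerve-damaging procedure. Section 10 presents this as background and does not say that it is the study treatment.

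**Conclusion.** The point holds in three parts of unequal weight.

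- **Certain and most important:** the treatment has two names. As written, group A's 40 children would receive a treatment other than the one the hypothesis names. This rests on explicit statements in sections 4 and 6 and needs no assumption. The documents do not show which name is correct.
- **Certain for the text shown, but lesser:** section 11 states no treatment risk and no mishap procedure for either modality. The entry exclusions are a partial safeguard.
- **Conditional:** if section 8 is applied as worded, any adverse event recorded in a child who then withdraws leaves the analysis. If the rule is meant for efficacy data only, there is no such loss, but the protocol does not say so.

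No numerical size can be given for the loss of harms, and the conclusion needs none. This should be fixed; the naming conflict comes first, because the risk statement depends on it.

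**What to change.** 1. Name the one intervention actually given, in the same words in sections 4, 6 and 10. Section 6 uses the past tense in places; if treatment has already been delivered, the text should state what was delivered, and the hypothesis should be reconciled with it openly.
2. In section 11, state that intervention's risks and the mishap procedure, including that sessions stop if an exclusion condition such as broken skin or a clotting disorder arises during treatment.
3. In section 8, limit the exclusion so that adverse events up to withdrawal are kept, as consent allows, and are reported by arm for all randomised children.

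The cost is wording in sections 4, 6, 8, 10 and 11, a short adverse event form if none is in use, and one safety table. The sample size and the outcome tests stay as they are. There is one downside: group B has no study sessions, so events there will be ascertained less often than in group A. This should be noted as a limitation wherever the arms are compared on safety.
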